8.5 Treatment of Overdose

The participant has taken (accidentally or intentionally) any drug administered as part of the protocol that exceeds the dose as prescribed by the protocol. It is up to the investigator or the reporting physician to decide whether a dose is to be considered an overdose, in consultation with the Sponsor.

8.6 Pharmacokinetics

The decision as to which plasma samples collected will be assayed for evaluation of PK/PD will be collaboratively determined by the Sponsor (e.g., samples at lower doses may not be assayed if samples at higher doses reveal undetectable drug concentrations). If indicated, these samples may also be assayed and/or pooled for assay in an exploratory manner for metabolites and/or additional PD markers.

8.6.1 Blood Collection for Plasma MK-8189

Sample collection, storage, and shipment instructions for plasma samples will be provided in the procedures manual.

8.6.2 Urine Collection for MK-8189 and metabolite profiling

Sample collection, storage, and shipment instructions for urine samples will be provided in the procedures manual.

8.7 Pharmacodynamics

Pharmacodynamic parameters, other than QTc and other ECG parameters, will not be evaluated in this study.

8.8 Biomarkers

Collection of samples for other biomarker research is also part of this study. The following samples for biomarker research are required and will be collected from all participants as specified in the SoA:

- Blood for Genetic Analysis

8.8.1 Planned Genetic Analysis Sample Collection

The planned genetic analysis sample will be drawn for CYP2C9 genotyping and for planned analysis of the association between genetic variants in DNA and drug response. If the IRB/IEC does not approve of the planned analysis of the association between DNA variation and drug response, or if there is a local law or regulation prohibiting the same, data analysis will be limited to CYP2C9. Leftover extracted DNA will be stored for future biomedical research if the participant signs the future biomedical research consent.

Sample collection, storage, and shipment instructions for planned genetic analysis samples will be provided in the procedures manual.

8.9 Future Biomedical Research Sample Collection

If the participant signs the future biomedical research consent, the following specimens will be obtained as part of future biomedical research:

- Leftover DNA for future research
- Leftover main study plasma from MK-8189 and/or metabolites assay stored for future research

8.10 Visit Requirements

Visit requirements are outlined in Section 1.3. Specific procedure-related details are provided in Section 8.

8.10.1 Screening

Within approximately 4 weeks prior to treatment allocation/randomization, potential participants will be evaluated to determine that they fulfill the entry requirements as set forth in Sections 5.1 and 5.2.

Participants may be rescreened after consultation with the Sponsor. Rescreening should include all screening procedures listed in the SoA, including consent review. Rescreen procedures cannot be conducted the day prior to treatment allocation/randomization if there are Day -1 procedures planned per protocol.

8.10.2 Treatment Period

Panel A: Healthy participants that meet selection criteria for enrollment will participate in Panel A, 16 participants in total. Participants will report to the CRU on Day -2 to undergo procedures in SoA.

Panel B and Panel D: Participants with schizophrenia that meet selection criteria for enrollment will participate in Panel B or Panel D, 16 participants or 20 participants, respectively, in total. Participants must be washed out from their antipsychotic medication for at least 5 days prior to the Day -1 Holter assessment. Participants will report to the CRU within a week of the start of their washout, minimally on Day -6.

Panel C: Participants with schizophrenia that meet selection criteria for enrollment will participate in Panel C, 12 participants in total. Participants will report to the CRU on Day -1 to undergo procedures in SoA.

On treatment days between Day 1 and Day 18 (Panel A, B and C) or Day 1 and Day 15 (Panel D), participants will be dosed once daily with MK-8189/placebo and have procedures

completed per the SoA. Participants will remain in the unit through Day 21 (Panel A, B, C) or Day 18 (Panel D) procedures and discharged at the discretion of the investigator.

8.10.3 Discontinued Participants Continuing to be Monitored in the Study

At any point if a participant discontinues from treatment but continues to be monitored in the study, a subset of study procedures specified in the SoA may be completed at the discretion of the investigator and with Sponsor agreement. The subset of study procedures completed will be communicated in a PCL.

8.10.4 Poststudy

After completion of treatment, participants in Panel B and Panel D will resume the use of their own antipsychotic medication after the Day 18, 48 hour post-dose (Day 20 - Panel B) or Day 15, 48 hour post-dose (Day 17 - Panel D) PK sample has been collected. A phone call should occur after 5-7 days after CRU discharge to check for any side effects and medication compliance.

All participants will be required to return to clinic approximately 14 days after the last dose of study intervention for the poststudy visit. If the poststudy visit occurs less than 14 days after the last dose of study intervention, a subsequent follow-up telephone call should be made at 14 days post the last dose of study intervention to determine if any AEs have occurred since the poststudy clinic visit.

8.11 Critical Procedures Based on Study Objectives: Timing of Procedure

For this study, the timing of the ECG extraction from the 24-hour Holter recording, and blood sample for MK-8189 and ECG collection are the critical procedures. At any postdose time point, these assessments will be collected close to the exact time point as possible. The PK sample should follow immediately after the Holter extraction is complete.

These procedures will be performed in the following order (below) with regard to the prescribed time. These procedures can be done prior to or after the time point.

1. Holter ECG assessment (extraction period)
2. Resting VS
3. Orthostatic VS
4. Blood for MK-8189

As a blood sample for assessment of MK-8189 plasma concentration, 12-lead safety ECGs, and resting and orthostatic VS are planned at the same timepoint, the order of execution is as follows:

1. 12-lead safety ECG

2. Resting VS
3. Orthostatic VS
4. Blood for MK-8189

All other procedures should be completed as close to the prescribed/scheduled time as possible. Study procedures can be performed prior or after the prescribed/scheduled time.

The order of priority can be changed during the study with joint agreement of the investigator and the Sponsor Clinical Director.

Any nonscheduled procedures required for urgent evaluation of safety concerns take precedence over all routine scheduled procedures.

The following variance in procedure collection times will be permitted.

- Predose standard safety evaluations: 12-lead safety ECGs within 2 hours prior to dosing; laboratory safety tests within approximately 48 hrs prior to dosing
- Postdose standard safety evaluations: 12-lead safety ECG, and VS
 - a. Day 1 postdose through Day 18 (Panels A, B and C) postdose or Day 1 postdose through Day 15 (Panel D) postdose may be obtained +/- 15 min of the theoretical sampling time
 - b. Day 19 postdose through Day 21 (Panels A, B and C) or Day 16 postdose through Day 18 (Panel D) may be obtained +/- 30 min of the theoretical sampling time
- Postdose laboratory safety tests on Days 1 through 18 may be obtained:
 - a. For blood: within -90 minutes from the theoretical sampling time
 - b. For urine: within -120 minutes from the theoretical sampling time.
- Predose and Postdose ECG Holter extractions may be obtained -15/+5 minutes from the theoretical sampling time.
- PK collections:
 - a. May be obtained -5/+10 minutes from the theoretical sampling time.
 - b. Must be obtained no more than +10 minutes after the end of the ECG Holter extraction window at each theoretical timepoint.
 - c. Must NOT be taken prior to the end of the ECG Holter extraction window.

- d. Must be obtained no more than +15 minutes after the 12-lead safety ECG at each theoretical timepoint and must be collected following vital sign assessments.
- Study intervention administration: +/- 30 mins

8.12 Study Design/Dosing/Procedures Modifications Permitted Within Protocol Parameters

This is a Phase 1 assessment of MK-8189 in humans, and the PK, PD, and safety profiles of the compound are still being elucidated. This protocol is written with some flexibility to accommodate the inherent dynamic nature of Phase 1 clinical studies. Modifications to the dose, dosing regimen, and/or clinical or laboratory procedures currently outlined may be required to achieve the scientific goals of the study objectives and/or to ensure appropriate safety monitoring of the study participants.

As such, some alterations from the currently outlined dose and/or dosing regimen may be permitted based on newly available data, but the maximum daily dose may not exceed those currently outlined in the protocol.

- Repeat of or decrease in the dose and/or titration steps of the study intervention administered in any given day/panel.
- Entire panel may be omitted.
- Adjustment of the dosing interval (e.g., divided doses [BID to QD, QD to BID, TID, or vice versa]).
- Instructions to take study intervention with or without food or drink may also be modified based on newly available data.
- Modification of the PK/PD sample processing and shipping details based on newly available data.
- A single dose may be skipped, and dosing may continue at the same dose level or adjusted downwards.

The PK/PD sampling scheme currently outlined in the protocol may be modified during the study based on newly available PK or PD data (e.g., to obtain data closer to the time of peak plasma concentrations). If indicated, these collected samples may also be assayed in an exploratory manner for metabolites and/or additional PD markers.

Up to additional 50 mL of blood may be drawn for safety, PK, and/or PD analyses. The total blood volume withdrawn from any single participant will not exceed the maximum allowable volume during his/her participation in the entire study (Section 10.10).

The timing of procedures for assessment of safety procedures (e.g., VS, ECG, safety laboratory tests, etc.) may be modified during the study based on newly available data.

Additional laboratory safety tests may be added to blood samples previously drawn to obtain additional safety information. These changes will not increase the number of study procedures for a given participant during his/her participation in the entire study.

It is understood that the current study may employ some or none of the alterations described above. Any alteration made to this protocol to meet the study objectives must be detailed by the Sponsor in a letter to the Study File and forwarded to the investigator for retention. The letter may be forwarded to the IRB/IEC at the discretion of the investigator.

9 STATISTICAL ANALYSIS PLAN

9.1 Statistical Analysis Plan Summary

This section contains a brief summary of the statistical analyses for this trial. Full detail is in the Statistical Analysis Plan (SAP) (Section 9.2).

Safety: Summary statistics and plots will be generated for raw laboratory safety tests, 12-lead ECGs, and/or VS as well as for change from baseline, as deemed clinically appropriate. Depending on the safety parameter, the difference from baseline will either be computed on the original scale (raw change from baseline) or on the log scale and back-transformed for reporting (percent change from baseline). For Panels A, B, and C, Day -1 8hr serves as a baseline for post-dose vital sign readings. For Panel D, Day -1 8 hr, 10 hr, and 16 hr readings will serve as time-matched baselines for the corresponding post-dose vital sign readings.

For all panels, summary statistics and plots will be generated for Barnes Akathisia Rating Scale (BARS), Abnormal Involuntary Movement Scale (AIMS) and Simpson Angus Scale (SAS), Bond and Leader Visual Analogue Scale (VAS), and Brief Psychiatric Rating Scale (BPRS) as well as for change from baseline. The difference from baseline will be computed on the original scale (raw change from baseline). Responses to the C-SSRS will be listed.

PK Summary:

Panel A (healthy participants: Japanese and non-Japanese) : Separately for each PK parameter, individual values of AUC_{0-24hr}, C_{max}, and C_{24hr} at each dose level (and day where applicable) will be natural log-transformed and evaluated with a linear mixed effects model containing a fixed effect for dose, population (Japanese, Non-Japanese), and population by dose and a random effect for subject.

Panels B and D (schizophrenia participants: monotherapy), Panel C (schizophrenia participants: add-on therapy); Separately for each panel and PK parameter, individual values of AUC_{0-24hr}, C_{max}, and C_{24hr} at each dose level (and day where applicable) will be natural log-transformed and evaluated with a linear mixed effects model containing a fixed effect for dose and a random effect for subject.

For each population and PK parameter, geometric means (GM) and corresponding ninety-five percent confidence intervals (CI) for each dose will be provided.

Cardiodynamic Analysis:

The exploratory objective pertaining to QTc will be evaluated through development of a model describing the relationship between MK-8189 plasma concentrations and QTc change from baseline. Separate models may be evaluated for each population. Details of the concentration-QTc analysis will be specified in a separate modeling analysis plan (MAP). This MAP will be completed prior to unblinding and database lock. Results of this analysis will be reported separately from the CSR.

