- a. Meals should be given at approximately the same time every day starting on Day -1 (time-matched to postdose meals) through Day 20. Breakfast will be given at ~1 hour postdose, lunch given at ~4 hours postdose, a snack given at ~8 hours postdose and dinner at ~12 hours postdose. All meals will follow the completion of all specified procedures at that timepoint.
- b. Panel A will be confined minimally from Day -2 through Day 21. Panel B will be confined within a week of starting their antipsychotic washout period through Day 21; minimally subjects will be confined from Day -6 through Day 21. Panel C will be confined minimally from Day -1 through Day 21.
- c. Single HR and BP measurements will be obtained at all postdose timepoints. On the following days, specific timepoints are noted:
- Day -1: Triplicate measurements time- matched to 8 hour post dose vital sign
 - Day 2 and Day 5: 8 hours post-dose (Panel A only)
 - Day 8, Day 11, Day 14 and Day 17: 8 hours post-dose
 - Day 10, Day 12, Day 13, Day 15, Day 16 and Day 18: 10 and 16 hours postdose
- d. Orthostatic assessments in HR and BP will follow semi recumbent vital sign assessments. Subjects should be standing for approximately 3 minutes prior to the orthostatic assessments. Orthostatic HR and BP measurements will be obtained on:
- Day -1: Time- matched to 8 hour post dose orthostatic vital sign.
 - Day 2 and Day 5: 8 hours post-dose (Panel A only).
 - Day 8, Day 11, Day 14 and Day 17: 8 hours post-dose
 - Day 10, Day 12, Day 13, Day 15, Day 16 and Day 18: 10 and 16 hours postdose
- e. For Panels A and B, single 12-lead safety ECG measurements will be at all postdose timepoints. On the following days, specific timepoints are noted:
- Day 1: Triplicate measurements within 2 hours prior to dosing.
 - Day 2 and Day 5: 8 hours post-dose (Panel A only).
 - Day 8, Day 11, Day 14 and Day 17: 8, 10 and 16 hours post-dose
- f. For Panels A and B, continuous (24-hour) Holter ECG measurements will be performed from approximately 30 minutes prior to dose administration and until 24 hours post-dose. ECG data will be extracted on:
- Day -1 (baseline measurement): time matched to dosing days at the following timepoints: 2, 6, 8, 10, 12, 16 and 24 hours
 - Day 7, Day 10, Day 13 and Day 16: predose, 2, 6, 8, 10, 12, 16 and 24 hours post-dose.
 - Day 18: 2, 6, 8, 10, 12, 16, 24, 36 and 48 hours post-dose.

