5.3.2 Caffeine, Alcohol, and Tobacco Restrictions

5.3.2.1 Caffeine Restrictions

Participants will refrain from consumption of caffeinated beverages or xanthine-containing products from 12 hours prior to the prestudy and poststudy visits.

On full PK sampling and/or Holter days (Panels A and B: Day -1, Day 7, Day 10, Day 13, Day 16, Day 18 and Day 19; Panel C: Day 9, Day 12, Day 15 and Day 18; Panel D: Day -1, Day 1, Day 4, Day 7, Day 10, Day 13, Day 15 and Day 16), participants will be permitted to consume approximately 2 units of caffeinated beverages or xanthine-containing products only between 1 hour and 2 hours post dose. Otherwise, participants will refrain from consumption of such products 8 hours prior to study drug administration until the 24- hour postdose ECG/PK assessment is complete.

On intermediate days, caffeinated beverages or xanthine-containing products will be limited to no more than 6 units per day amounts (>6 units: 1 unit = 120 mg of caffeine).

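### Panels A–C: most vital-sign changes at 16–24 mg (12 of 15 timed readings) are taken at 10 h or 16 h against an 8 h baseline, with no same-hour placebo difference planned

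*Combined protocol and SAP*

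**What the plan says.** Section 9.1 sets the rule: "For Panels A, B, and C, Day -1 8hr serves as a baseline for post-dose vital sign readings". For Panel D the same section uses separate Day -1 readings at 8, 10 and 16 h, each matched to its own post-dose hour. Section 9.4 also places the vital-sign baseline on Day -1.

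The Schedule of Activities (Section 1.3, footnotes c and d for Panels A, B and C) shows what is collected. For resting heart rate and blood pressure: "Day -1: Triplicate measurements time- matched to 8 hour post dose vital sign". For standing readings: "Day -1: Time- matched to 8 hour post dose orthostatic vital sign". The later post-dose schedule for both includes: "Day 10, Day 12, Day 13, Day 15, Day 16 and Day 18: 10 and 16 hours postdose". The remaining timed readings are at 8 h, on Days 8, 11, 14 and 17, plus Days 2 and 5 in Panel A only.

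Sections 9.1 and 9.6 plan descriptive summaries and plots of raw values and of change from baseline. Neither specifies a between-arm vital-sign difference. Section 9.1 sends the reader to Section 9.2 for full detail, but that section covers only who is responsible for the analyses.

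**The concern.** A change score removes stable differences between people. It does not remove a difference between the hour of the baseline and the hour of the follow-up reading. Doses are given in the morning (Section 8.1.9.1), so 16 h falls late in the evening or at night. Meal state differs too, with "a snack given at ~8 hours postdose and dinner at ~12 hours postdose": the 10 h reading comes about 2 h after the snack, and the 16 h reading about 4 h after dinner. Any off-drug shift between 8 h and these hours enters the within-group change in full and could mask or mimic a drug effect.

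The hour also changes with the dose. The lower doses have only 8 h readings, while the higher doses have mostly 10 h and 16 h readings. Vital signs are among the primary endpoints, and Section 4.2 says that doses above 12 mg were of particular interest when these panels were designed.

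**Working it through.** The plan gives no SD, shift or precision figure for vital signs, so there is no stated number to reproduce.

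**1. Counting the readings.** Inputs are footnotes c and d in Section 1.3 and the titration days in Section 4.1 (16 mg Days 10–12, 20 mg Days 13–15, 24 mg Days 16–18).

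| Dose | 8 h | 10 h | 16 h | Timed readings |
|---|---|---|---|---|
| 4–12 mg, Panel A | 3 (Days 2, 5, 8) | 0 | 0 | 3 |
| 4–12 mg, Panels B and C | 1 (Day 8) | 0 | 0 | 1 |
| 16 mg | 1 (Day 11) | 2 (Days 10, 12) | 2 | 5 |
| 20 mg | 1 (Day 14) | 2 (Days 13, 15) | 2 | 5 |
| 24 mg | 1 (Day 17) | 2 (Days 16, 18) | 2 | 5 |

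At 16–24 mg there are 15 timed readings, of which 6 days × 2 = 12 (80%) have no Day -1 reading at the same hour. Standing readings follow the same schedule. The count describes the planned titration; participants held or taken down in dose would differ.

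**2. What the change score contains.** Let the drug effect be e and the off-drug shift from 8 h to the later hour be s. Expected change is e + s on active and s on placebo, so the same-hour difference is e. With assumed values e = +10 and s = −5, the active change shows +5 and the difference shows +10. Between two doses at the same hour, (e₂ + s) − (e₁ + s) = e₂ − e₁, so the shift cancels if it is stable across days.

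**3. Precision of the placebo difference.** Planned sizes are 12 vs 4 (A), 12 vs 4 (B) and 9 vs 3 (C), from Section 6.3.1. SE/SD = √(1/a + 1/p), with a active and p placebo; the 95% half-width is t × SE.

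- A or B: √(1/12 + 1/4) = 0.577; t(14) = 2.145; half-width 1.24 SD.
- C: √(1/9 + 1/3) = 0.667; t(10) = 2.228; half-width 1.49 SD.
- A–C pooled, adjusted for panel: the sum of ap/(a + p) is 3 + 3 + 2.25 = 8.25; SE = 1/√8.25 = 0.348; t(40) = 2.021; half-width 0.70 SD.

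Assuming an SD of change of 8–12 mmHg, the half-widths are 9.9–14.9, 11.9–17.8 and 5.6–8.4 mmHg.

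**4. When subtraction helps.** Mean squared error is SD²/a + s² for the raw active change and SD²/a + SD²/p for the difference. The difference is better only if |s| exceeds SD/√p: 0.50 SD in A or B (p = 4), 0.58 SD in C (p = 3) and 0.30 SD pooled (p = 11). At the assumed SDs these are 4–6, 4.6–6.9 and 2.4–3.6 mmHg.

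Steps 3 and 4 assume complete data and a common SD. Pooling also assumes a similar drug effect in each panel.

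**The case against.** The trial tests no hypotheses, and the baseline rule is openly stated. Raw values are summarised as well as changes, and data are analysed by treatment received (Section 9.5), so placebo values at the same day and hour will exist. What is missing is a planned subtraction, not control data. Each of the three higher doses keeps one 8 h reading, and 12 mg has one on Day 8, so a like-for-like hour is available across the step. Titration decisions (Section 6.6) use the individual participant's safety data, not group mean change. All of this stands, and it keeps the point minor.

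Three stronger readings are tempting, but the documents do not support them.

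- **Caffeine.** A reader might infer that the 8 h readings in A and B are also compromised. Section 5.3.2.1 lists "Panels A and B: Day -1, Day 7, Day 10, Day 13, Day 16, Day 18 and Day 19" as restricted days, which leaves out Days 8, 11, 14 and 17. But the rule limits allowance; it does not measure intake. Panel D is affected in the same way: 20 of its 33 timed readings fall on days not listed for it. For Panel C the list reads "Panel C: Day 9, Day 12, Day 15 and Day 18" and does not classify Day -1. None of this shows bias.
- **Orthostatic data.** A reader might treat these as equally affected. Each standing reading follows a semi-recumbent one at the same timepoint (footnote d; Section 8.3.3.3), so standing minus resting can be computed at every hour without Day -1.
- **Heart rate.** A reader might say that a matched source is being ignored, since Holter in A and B has "Day -1 (baseline measurement): time matched to dosing days at the following timepoints: 2, 6, 8, 10, 12, 16 and 24 hours". Section 9.4 already lists heart rate as an exploratory cardiodynamic endpoint, and the concentration-QTc details sit in a separate modeling plan that is not in these documents. Whether Holter heart rate is covered there cannot be judged.

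**Conclusion.** The mismatch is real and follows directly from the schedule: in each of Panels A, B and C, 12 of 15 timed resting readings at 16–24 mg lack a baseline at the same hour, while every timed reading at 4–12 mg has one. Change from baseline across the 12-to-16 mg step therefore mixes dose with clock hour whenever the 10 h and 16 h readings are used.

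It would be wrong to infer that the vital-sign results at these doses are biased by a known amount or cannot be interpreted. The documents give neither the size nor the direction of any shift. A concurrent placebo group exists, and comparisons among 16, 20 and 24 mg at a fixed hour are not affected if the shift is stable across days. Nor is the placebo difference always the better estimate: within one panel it reduces mean squared error only if the shift exceeds about half an SD.

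The conclusion is a minor improvement in reporting, of most use for blood pressure.

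**What to change.** In Sections 9.1 and 9.6, for the 10 h and 16 h vital signs in Panels A–C:

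1. Label raw changes from baseline as not time-matched.
2. Beside them, show the active-minus-placebo difference in change at the same day and hour with its 95% CI, for each panel and pooled across A–C with adjustment for panel. Describe it as a descriptive estimate and keep the raw summaries.
3. For orthostatic data, also summarise standing minus resting at the same hour.

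The cost is SAP wording and extra table columns, using data already collected. The drawbacks are the wide intervals within single panels and, for the pooled estimate, the assumption of similar drug effects in healthy participants, washed-out patients and patients on background antipsychotics. Both should be stated next to the table.
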